8.2 Adverse Device Effect (ADE)

An adverse event related to the use of a medical device.

This definition includes adverse events resulting from insufficient or inadequate instructions for use, deployment, implantation, installation, or operation, or any malfunction of the medical device.

This definition includes any event resulting from the use error or from intentional misuse of the medical device.

During this clinical investigation an event should be considered related to the device when it is the result of:

- The device components (e.g. lead, extension, Trial Simulator, Remote).
- The Therapy/simulation.

8.3 Unanticipated serious adverse device effect (USADE)

An unanticipated serious adverse device effect (USADE) is a serious adverse device effect that was not previously identified in nature, severity, or degree of incidence in the investigational plan or application (including a supplementary plan or application), or any other unanticipated serious problem associated with a device that relates to the rights, safety, or welfare of subjects.

Those known adverse events related to the device, procedure or therapy is listed in the Risk Analysis section.

8.4 Anticipated serious adverse device effect (ASADE)

A serious adverse device effect which by its nature, incidence, severity or outcome has been previously identified in the risk analysis report.

Untoward medical occurrences that are not unanticipated, i.e. are unsurprising, are identified in the Physician Manual or CIP and ICF.

8.5 Device Deficiency

PRF is a CE marked (as well as TGA and FDA approved) device which meets vigilance reporting criteria. Device Deficiencies will be handled under the post-market surveillance / vigilance system from the Sponsor.

8.6 Serious adverse device effect

Adverse device effect that has resulted in any of the consequences characteristic of a serious adverse event.

8.7 Severity

The Investigator will use the following definitions to rate the severity of each adverse event:

- Mild: Awareness of a sign or symptom that does not interfere with the subject's usual activity or is transient, resolved without treatment and no sequelae.

- Moderate: Interferes with the subject's usual activity or requires symptomatic treatment.
- Severe: Symptom(s) causing severe discomfort with significant impact of the subject's usual activity and requires treatment.

8.8 Reporting.

According to current regulations, professionals must report those incidents that are associated with a medical device or with the information provided with the product and that incident is such that it has caused death or a serious deterioration in health, or if it occurs again it can cause them.

An incident is understood to be any malfunction, failure or deterioration of the characteristics or operation of a product, as well as any deficiency in the labelling or in the instructions for use that could or have led to death or serious deterioration of the condition health of a patient or a user. The types of adverse incidents that must be reported are the following:

1. Those that lead to death.
2. Those that give rise to a serious deterioration of the state of health of the patient, user or other person, such as:

- Illness or injury with threat to life.
- Permanent deterioration of a bodily function or permanent damage to a body structure.
- Process that requires medical or surgical intervention to avoid permanent deterioration of a bodily function or permanent damage to a body structure.

3. Potential incidents, which are those that could have led to death or a serious deterioration of health, but that have not occurred due to fortunate circumstances or the intervention of health personnel.

These incidents must be reported by the investigators. They must notify the sponsor of any serious incidents that may be related to the devices involved in the development of the investigation, through Annex III available at:

<https://www.aemps.gob.es/vigilancia/productosSanitarios/vig-prof-nota.htm#II>

And the sponsor must evaluate them and notify them to the surveillance points of medical devices of the CCAA, in accordance with the general guidelines established by the Medical Device Surveillance System for the notification of adverse incidents:

<https://www.aemps.gob.es/surveillance/healthproducts/professional-monitoring.htm>

The Sponsor contact information for these events is:

[name] [name],

E-mail: [contact]

Table1. Schedule

Assessment								
Visit	Screening	Baseline	Treatment	1 month	2 months	4 months	6 months	Unscheduled
Window		Within 30 days from screening	± 15 days	± 7 days	± 14 days	± 14 days	± 20 days	
Pregnancy Test	X							
Sign Informed Consent	X							
Entry Criteria Evaluation	X	X						
Demographics	X							
Medical History	X	X						
Randomization		X						
Treatment Process			X					
Pain and Surgical History	X							
Medication Usage	X		X	X	X	X	X	X
VAS questionnaire		X		X	X	X	X	X
ODI questionnaire		X		X	X		X	X
SF-12 questionnaire		X		X	X	X	X	X
DN4 questionnaire		X		X	X		X	X
PGI-I questionnaire				X	X	X	X	X
Subject questionnaire of treatment satisfaction					X		X	X
AP and Lateral radiography imaging		X						
Deviation Monitoring			X	X	X	X	X	X
Adverse Event Monitoring		X	X	X	X	X	X	X
Screening Failures		X						
Study Completion			X				X	X

9. - TREATMENT DESCRIPTION

Both treatments (control group and experimental group) will always be performed in an ambulatory environment through sedation and anaesthesia.

The lower back and buttocks will be prepared for an aseptic technique. Lateral and AP views of the sacral foramina and hiatus will be taken and the entry point for the epidural needle will be marked on the surface of the skin, 1-2 cm caudal to the sacral hiatus. The skin and subcutaneous tissue underlying the entry site will be anesthetized using 1-2 ml of 1% lidocaine.

A 9-cm-long, 16-gauge (ga) epidural needle (Cosman RCE-C916S-P) is inserted through the skin and into the caudal canal, 1-2 cm beyond the sacral hiatus, ending at an angle of approximately 15° concerning the skin. Intravascular and subdural placement will be ruled out by injecting 1-1.5 ml of non-ionic radiographic contrast (180 mg of iohexol per ml) through the fluoroscopic needle *in vivo*.

9.1 Control Group. Epidural Steroids Injection.

A radiopaque, guidable radiofrequency electrode (Cosman RCE-E401519-P) will bend slightly at a 45° angle proximal to its metal tip and then be inserted through the needle. The electrode shall include an active 20/15 mm gauge tip, a 19/40 cm gauge shaft, a rounded distal point temperature sensor, an injection port and an integral generator connection. The electrode will be visualized by fluoroscopy as it is guided in the epidural space from the sacral canal to the lumbar vertebral canal.

The electrode will be connected to an output of the RF generator (Cosman RFG-4-120V/GF RF Generator). To provide a monopolar PRF operation, a ground pad (Cosman DGP-PM-10) will be placed on a shaved muscle part of the posterolateral thigh skin and connected to the reference socket of the RF generator with voltage 0 for 240 seconds (to ensure single-blind).

Intravascular and subdural placement will be ruled out by injecting 1-1.5 ml of non-ionic radiographic contrast (180 mg of iohexol per ml) through the integral injection port of the electrode under live fluoroscopy. Subsequently, betamethasone 12 mg will be administered.

After treatment, the needle and electrode will be removed. A sterile dressing will be applied over the needle insertion site. The patient will be monitored (visualized by fluoroscopy) while the sedation is removed, the motor dysfunction of the leg is verified and then the patient will be discharged.

9.2 Experimental Group. Epidural Pulsed Radiofrequency.

A radiopaque, guidable radiofrequency electrode (Cosman RCE-E401519-P) will bend slightly at a 45° angle proximal to its metal tip and then be inserted through the needle. The electrode shall include an active 20/15 mm gauge tip, a 19/40 cm gauge shaft, a rounded distal point temperature sensor, an injection port and an integral generator connection. The electrode will be visualized by fluoroscopy as it is guided in the epidural space from the sacral canal to the lumbar vertebral canal. The electrode will be connected to an output of the RF generator (Cosman RFG-4-120V/GF RF Generator). To provide a monopolar PRF operation, a ground pad (Cosman DGP-PM-10) will be placed on a shaved muscle part of the posterolateral thigh skin and connected to the reference socket of the RF generator.

The active tip of 15 mm of the electrode will be placed in the internal aspect of the pedicle in each of levels L4, L5 and / or S1, on the right or left side, according to the patient's pain distribution (Figure 1). Intravascular and subdural placement will be ruled out by injecting 1-1.5 ml of non-ionic radiographic contrast (180 mg of iohexol per ml) through the integral injection port of the electrode under live fluoroscopy. At each treated level, motor stimulation (50 Hz, 1 ms) of less than 0.4 volts will reproduce the patient's pain and motor stimulation (2 Hz, 1 ms) of less than 0.6 volts will result in a contraction muscle in the leg. The pulsed radiofrequency will be applied for 240 seconds (4 minutes), where the pulses of 45 volts and 20 milliseconds (ms) will be administered at 2 Hz (pulses per second) and the pulse width will be regulated to maintain the temperature at 42 °C or less. (E-dose = Vary Width). The steady-state impedance and current will be measured for each PRF epidural treatment at L5 and S1 levels using the 20-gauge, 15 mm active tip.

After the experimental treatment, the needle and electrode will be removed without injecting or any other substance capable of producing pain relief. A sterile dressing will be applied over the needle insertion site. The patient will be monitored while the sedation is removed, the motor dysfunction of the leg is verified and then the patient will be discharged.

10. - PRACTICAL CONSIDERATIONS AND ETHICAL ASPECTS

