5.3 Secondary Endpoints

- 5.3.1. Change from Baseline in pain at 1, 2 and 4 months (assessed by Visual Analogue Scale, VAS).
- 5.3.2. Change from Baseline in disability at 1, 2 and 6 months (assessed by Oswestry Disability Index, ODI).
- 5.3.3. Change from Baseline in health survey at 1, 2, 4 and 6 months (assessed by Short Form Health Survey, SF-12).
- 5.3.4. Change from Baseline in neuropathic pain at 1, 2 and 6 months (assessed by Douleur Neuropathique 4 Questions, DN4).
- 5.3.5. Assessment of improvement of pain with experimental procedure at 1, 2, 4 and 6 months (assessed by Patient Impression of Improvement, PGI-I).
- 5.3.6. Incidence of unanticipated adverse device effects.
- 5.3.7. Change in opioid intake in 6 months.
- 5.3.8. Adverse events related to procedures (experimental group and control group).
- 5.3.9. Assessment of subject satisfaction with experimental procedure at 2 and 6 months.

6. - ELIGIBILITY CRITERIA

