7.2 Randomization Process

The clinical investigation will be single-blind. The assignment to the type of surgical treatment is carried out randomly and open for the investigators but not for

the patients. Randomization will be done with concealment of the randomization sequence and it takes place after informed consent has been signed.

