8.1 Adverse Events

The following adverse events will be recorded in the eCRF of the study:

- All serious adverse events.
- All adverse events considered of interest for this study, regardless of their seriousness.

NOTE - As the primary efficacy measure in this study is pain, leg and back pain does not need to be reported as an adverse event unless it meets the definition of a serious adverse event. However, Investigators may, at their discretion, report any pain-related adverse events during the study.

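### The severity grades in section 8.7 are not mutually exclusive: a transient, untreated event that interferes with activity is both Mild and Moderate, and no rule tells the unblinded investigator which applies

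*Combined protocol and SAP*

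**What the plan says.** Section 8.7 opens with "The Investigator will use the following definitions to rate the severity of each adverse event" and gives three definitions:

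- For the lowest grade, Mild, the text is "Awareness of a sign or symptom that does not interfere with the subject's usual activity or is transient, resolved without treatment and no sequelae".
- For the middle grade, Moderate, it is "Interferes with the subject's usual activity or requires symptomatic treatment".
- For the highest grade, Severe, it is "Symptom(s) causing severe discomfort with significant impact of the subject's usual activity and requires treatment".

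It does not say what to do when an event fits more than one. On who knows the allocation, section 7.2 says "The assignment to the type of surgical treatment is carried out randomly and open for the investigators but not for", with the patients named as the blinded party. No blinded grading or adjudication of severity is described. The DSMB in section 3.8 supervises safety but is given no grading role in the protocol text.

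Three other places set how far the grades reach. Section 8.1 limits eCRF recording to serious adverse events and "All adverse events considered of interest for this study, regardless of their seriousness". It also exempts leg and back pain from reporting unless serious, though investigators may report it. Section 8.1.1 defines seriousness without using the severity grade, and lists the events of interest as procedures longer than one hour, surgical wound problems and infection. Section 8.3 treats a serious device effect as unanticipated if it "was not previously identified in nature, severity, or degree of incidence in the investigational plan", and section 8.4 also refers to severity. Unanticipated device effects are secondary endpoint 5.3.6.

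**The concern.** The definitions mix three things: how bad the event was, how long it lasted, and whether it needed treatment. Mild and Moderate each join their conditions with an or, while Severe joins its conditions with an and. The second limb of Mild sets no ceiling on interference, so an event that stopped the patient's usual activity can be graded Mild if it passed quickly, untreated and without sequelae. The same event is also Moderate. At the other end, need for treatment is a precondition for Severe, however bad the event was.

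Where two grades are both correct, monitoring cannot call either one an error. Because the person choosing knows the arm, the choice could lean differently in the two groups without breaching the protocol. At stake is the consistency of any severity listing by arm and, if the 8.7 grade is what sections 8.3 and 8.4 mean by severity, the line between anticipated and unanticipated serious device effects.

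**Working it through.** The plan states no figure on this point, so there is none to reproduce. The check codes the three definitions in section 8.7 as logical rules and lists every combination of their inputs.

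**Inputs.** Interference I (none / some / significant), severe discomfort D (yes/no), transient T (yes/no), requires treatment R (yes/no), sequelae S (yes/no). Profiles: 3 × 2 × 2 × 2 × 2 = 48. Resolving without treatment is coded as the opposite of requiring treatment.

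**Rules.**
- Moderate = I is some or significant, OR R.
- Severe = D AND I significant AND R.
- Mild, reading A = I none, OR (T AND not R AND not S).
- Mild, reading B = (I none OR T) AND not R AND not S. Here the untreated and no-sequelae conditions govern both limbs.

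**Mild and Moderate together.**
- No interference but treatment required (reading A only): 2 (D) × 2 (T) × 2 (S) = 8.
- Interference, transient, no treatment, no sequelae (both readings): 2 (I) × 2 (D) = 4.
- Reading A: 8 + 4 = 12 of 48. Reading B: 4 of 48.

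**No grade at all (reading B only).** No interference, no treatment, sequelae present: 2 (D) × 2 (T) = 4.

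**Moderate and Severe together.** 2 (T) × 2 (S) = 4 on either reading. This is ordinary nesting and is not counted as an ambiguity.

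| Grades met | Reading A | Reading B |
|---|---|---|
| Mild and Moderate | 12 | 4 |
| Moderate and Severe | 4 | 4 |
| Exactly one | 32 | 36 |
| None | 0 | 4 |
| Total | 48 | 48 |

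**Severe discomfort, significant impact, no treatment required.** 2 (T) × 2 (S) = 4 profiles, with the same result on both readings: the transient one without sequelae is Mild and Moderate, the other three are Moderate only, and none is Severe.

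**Reach.** Set beside sections 8.1 and 8.1.1, the overlap matters only for events that are recorded. Of the listed events of interest, a long procedure is not a symptom, and a treated infection cannot use the transient/untreated route to Mild. That leaves mainly wound problems, together with serious events. For example, a patient admitted only for observation, whose symptom passes untreated without sequelae, could have a serious event graded Mild. The statistical section (section 13) plans no analysis by severity.

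**The case against.** The strongest case against is that little depends on these grades. That largely stands, and it rules out several stronger readings.

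- A reader might infer that brief non-serious leg weakness after the procedure will be under-graded. It is not a listed event of interest, so on the text of section 8.1 it need not be recorded. If it is serious, section 8.1.1 captures it whatever its grade.
- A reader might infer bias in the procedure-related adverse event endpoint (5.3.8) or in DSMB supervision. Endpoint 5.3.8 carries no grade, section 13 plans no severity analysis, and section 3.8 does not mention grades. The only endpoint link is the severity criterion in sections 8.3 and 8.4, which concerns events already classed as serious.
- A reader might infer that an incapacitating event left untreated can never be Severe. The definition turns on requiring treatment, not on receiving it. An investigator could hold that treatment was required but not given. The bar applies only to events that do not require treatment, and this room for argument adds to the discretion.
- A reader might infer that a non-interfering wound symptom needing treatment is both Mild and Moderate. That holds on reading A only; on reading B it is Moderate alone.

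It can also be said that a single highest-grade rule would settle every double grade. It would, but it would leave the bar on Severe and, on reading B, the four ungraded profiles.

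None of this removes the core defect. On both readings, one and the same event meets two grades with no rule between them.

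**Conclusion.** The point holds in limited form. Section 8.7 asks for a grade for each adverse event, and for a definable class of events its definitions return two. It also keeps events with severe discomfort and significant impact that need no treatment out of Severe. The grading investigator knows the arm, so a difference between arms in how these events are graded is possible. The documents show that risk, not an actual bias.

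The size is 12 of 48 logical profiles with both Mild and Moderate on reading A and 4 of 48 on reading B, with 4 more ungraded on B. These counts depend on the grid chosen and say nothing about how often such events occur; the plan gives no event rates. The practical effect is confined to recorded events and, assuming severity in sections 8.3 and 8.4 means the 8.7 grade, to the unanticipated classification behind endpoint 5.3.6. Seriousness and the primary VAS comparison are not affected. It is a modest defect, worth correcting because correction costs almost nothing.

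**What to change.** In section 8.7 and the adverse event CRF instructions:

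1. State that the grade reflects intensity and interference with usual activity at the event's worst.
2. Delete from Mild the limb on being transient, untreated and without sequelae.
3. Delete the treatment condition from Severe.
4. Add: *if more than one definition applies, the highest grade is assigned.*
5. Record duration, treatment given and sequelae as separate CRF fields, so that no information is lost.

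Applied to the 48 profiles with Moderate otherwise unchanged, every profile gets one final grade:
- Mild: no interference and no treatment, 2 × 2 × 2 = 8.
- Severe: severe discomfort with significant impact, 2 × 2 × 2 = 8.
- Moderate: the remaining 48 − 8 − 8 = 32.

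If the sponsor wants no treatment element in the grade at all, the treatment limb of Moderate can go too. The 8 non-interfering treated profiles then become Mild.

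The cost is a wording change, with no new visit, test or patient. The downside is that some events now gradable as Mild would be reported higher, and severe-impact events that need no treatment would move to Severe, so the safety table may look slightly less favourable. The change narrows the investigator's discretion but leaves the grader unblinded. Removing that as well would need grading or review by someone who does not know the arm.

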All information concerning the study device supplied by Fundación Investigación HM Hospitales in connection with this study, and not previously published, is considered confidential and proprietary information. This information includes the clinical investigation plan, subject informed consent and case report forms. This confidential information shall remain the sole property of Fundación Investigación HM Hospitales, shall not be disclosed to others without prior written consent from Fundación Investigación HM Hospitales and shall not be used except in the performance of this study.

The information developed during the conduct of this clinical study is also considered confidential and will be used by Fundación Investigación HM Hospitales in connection with the development of the study device. This information may be disclosed as deemed necessary by Fundación Investigación HM Hospitales.

The below-named individuals are authorized to sign this clinical investigation plan and its amendments.

_____ / _____ / _____

Signature

Date

Printed Name

Title

1. - SUMMARY

1. Study Title:	Epidural Pulsed Radiofrequency versus Epidural Steroids Injection for Treatment of Failed Back Syndrome: A Prospective, Randomized, Single-Blind and Multicenter Study
2. Sponsor:	Fundación Investigación HM Hospitales
3. Type of Clinical Investigation:	Clinical Investigation with CE-marked medical devices.
4. Coordinating Investigator:	[name] [name], MD PhD.
5. Protocol Code:	EPIPUL
6. Geography	Spain
7. Clinical Sites:	
Hospital Universitario Puerta de Hierro (Madrid, Spain).Hospital Universitario Rey Juan Carlos (Madrid, Spain).Hospital Universitario de Sanchinarro (Madrid, Spain)Hospital Fremain Majadahonda (Madrid, Spain)Hospital Universitario La Fé (Valencia, Spain)Hospital Clínico Universitario de Santiago (Santiago de Compostela, Spain)
8. Study Purpose:	The present pilot study suggests that the epidural application of PRF to the dorsal roots and proximal DRG can be safe and effective in the treatment of intractable pain after back surgery. Several explanatory hypotheses motivate further study of this apparent improvement over transforaminal PRF, which has produced inconsistent results in published reports to date.
9. Treatments	Experimental Group (62 patients): Epidural radiofrequency by catheter in the epidural space plus steroids administration. Control Group (62 patients): Epidural steroids injection.

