10. Primary Endpoint:	Difference in pain reduction between the control group and the experimental group since the baseline visit and the 6 month visit evaluated by Visual Analogue Scale (VAS).
11. Secondary Endpoints:	
Change from Baseline in pain at 1, 2 and 4 months (Visual Analogue Scale, VAS).Change from Baseline in disability at 1, 2 and 6 months (assessed by Oswestry Disability Index, ODI).Change from Baseline in health survey at 1, 2, 4 and 6 (assessed by Short Form Health Survey, SF-12).Change from Baseline in neuropathic pain at 1, 2 and 6 months (assessed by Douleur Neuropathique 4 Questions, DN4).Change from Baseline in improvement of pain at 1, 2, 4 and 6 months (assessed by Patient Impression of Improvement, PGI-I).Assessment of subject satisfaction with experimental procedure 2 and 6 months.Incidence of unanticipated adverse device effects.Change in opioid intake in 6 months.Adverse events related to procedures (experimental group and control group).
12. Study Design:	Prospective, randomized, single-blind and multi-centre study. Controlled comparison between epidural steroids injection with catheter and epidural radiofrequency by catheter in the epidural space plus steroids administration. After the treatment, patients will be followed-up at 1, 2, 4 and 6 months.

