5.1 Hypothesis

This clinical investigation will intends to demonstrate reduction of chronic lumbar radicular pain following back surgery by epidural application of temperature-

controlled PRF to the dorsal radicular filaments proximal to the DRG and dorsal nerve root in the epidural space using a guidable, radio-opaque, catheter electrode (Boston Scientific RCE) having an elongated 15-mm active tip and a temperature sensor at its rounded distal point (Cosman RCE-E401519-P) versus epidural steroids injection.

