7.3 Sample Size and justification

Pain reduction at least thirty millimeters between the baseline visit and the 6 months visit in patients assigned to the experimental group evaluated by the Visual Analogue Scale (VAS). Pain reduction of twenty millimeters less in the experimental group than in the control group since the baseline visit and the 6 months visit evaluated by the Visual Analogue Scale (VAS).

To achieve a power of 90.00% to detect differences in the contrast of the null hypothesis $H_0: \mu_1 = \mu_2$ through a bilateral T-Student Test for two independent samples, taking into account that the level of significance is 5%, and assuming that the mean of the difference in VAS of the 6-month radiofrequency plus steroid group is 40 mm, the average of the control group is 60 mm and the standard deviation of both groups is 30 mm, with an estimate of losses of the 20%, it will be necessary to include 62 patients per group, total of 124 patients.

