11.1 Insurance Policy

According with current clinical trial legislation, this clinical trial does not require an insurance policy since the devices under study are used under the authorized conditions of use and the study does not imply an increase in the risk to the patient.

12. - PUBLICATIONS RIGHTS

Principal Investigator shall have the right to publish the results of the Study in any abstract, paper, presentation or manuscripts (not limited enumeration).

Principal Investigator shall give BOSTON SCIENTIFIC a reasonable period of 30 (thirty days) to review and comment upon an intended publication of Principal Investigator regarding the results of the Study prior to publication, to determine if any Intellectual Property Rights and/or Confidential Information should be removed. BOSTON SCIENTIFIC shall respond promptly in writing to Principal Investigator with any comments or objections, setting forth such information in reasonably sufficient detail.

Principal Investigator shall consider BOSTON'S SCIENTIFIC comments and/or objections in good faith and shall cause any and all appropriate changes to be made prior to further distribution and publication.

13. - STATISTIC ANALYSIS

A descriptive analysis of the categorical variables was performed using absolute and determined frequencies; and in the numerical variables, through the mean and

standard or median deviation and 25th and 75th percentiles, according to compliance with the assumption of normality.

The analysis of the main variable, pain difference between baseline measurement and 6 months after treatment in the radiofrequency group plus steroids vs steroids, will be carried out using a contrast of means with the t-Student or U Mann-Whitney test in case of not being able to fulfill the corresponding assumptions.

The size of the effect is estimated with Cohen's letter, interpreting a Cohen's letter <0.01 as "very small", between 0.01 to 0.2 as a "small" effect, around 0.5 an "average" effect ", from 0.8 to infinity, a" large "effect, according to the categorization of Cohen and Sawilowsky (Cohen, Jacob (1988). Statistical analysis of power for behavioral sciences. Routledge; Sawilowsky, S (2009). "New effect size rules of thumb". Journal of Modern Applied Statistical Methods. 8 (2): 467–474.).

If the imbalance is observed between the two groups, linear regression will be executed to adjust for variables that are observed unbalanced between them.

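### The experimental arm is defined and analysed as radiofrequency plus steroids, but its only written procedure (Section 9.2) contains no steroid step

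*Combined protocol and SAP*

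**What the plan says.** Four places describe the experimental arm or the analysed contrast as an add-on to steroid:

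- Summary item 9 (Treatments), experimental group: "Epidural radiofrequency by catheter in the epidural space plus steroids administration".
- Summary item 12 (Study Design): "Controlled comparison between epidural steroids injection with catheter and epidural radiofrequency by catheter in the epidural space plus steroids administration".
- Section 7.3 (sample size): "the mean of the difference in VAS of the 6-month radiofrequency plus steroid group is 40 mm".
- Section 13 (primary analysis): "pain difference between baseline measurement and 6 months after treatment in the radiofrequency group plus steroids vs steroids".

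The procedures are in Section 9. Its opening text covers both arms, beginning "Both treatments (control group and experimental group) will always be performed in an ambulatory environment through sedation and anaesthesia", and includes skin lidocaine and radiographic contrast but no steroid. Section 9.1 (control) adds the catheter electrode, a zero-voltage period of 240 seconds, contrast, and then: "Subsequently, betamethasone 12 mg will be administered". Section 9.2 (experimental) lists electrode placement, contrast, stimulation, PRF for 240 seconds and removal. It mentions no steroid and ends: "After the experimental treatment, the needle and electrode will be removed without injecting or any other substance capable of producing pain relief".

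The study title and the hypothesis in Section 5.1 set PRF "versus epidural steroids injection" or equivalent, without saying that the PRF arm also receives steroid. Section 7.1 words the comparison differently again and brings in transforaminal placement.

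**The concern.** Adding PRF to steroid and replacing steroid with PRF are different treatments and answer different questions. In the first, the arms differ only in PRF, and the zero-voltage control procedure isolates its effect. In the second, the arms differ in PRF and in steroid, and the observed difference is the PRF effect net of the steroid effect that was withheld.

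The plan sizes and analyses the first and gives operating instructions for the second. Section 10.1 asks investigators to comply strictly with the protocol, and under Section 7.2 they know the allocation, so the text of 9.2 can directly determine what is injected. Six sites are listed. If some follow 9.2 and others follow the Summary, the pooled mean difference is a blend of the two contrasts, in proportions set by site practice. Unless the injected substance is recorded for each patient, the analysis cannot separate them.

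**Working it through.** **Step 1. Where a steroid is specified.**

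| Place | Steroid in the experimental arm? |
|---|---|
| Summary item 9 | Yes, no drug or dose |
| Summary item 12 | Yes, no drug or dose |
| Section 7.3 | Yes, no drug or dose |
| Section 13 | Yes, no drug or dose |
| Title, Section 5.1 | Not stated, not excluded |
| Section 7.1 | Not stated |
| Section 9, text common to both arms | No step |
| Section 9.1 (control only) | Betamethasone 12 mg, for controls |
| Section 9.2 | No step |

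Steroid steps in the procedures: one in 9.1, none in 9.2, none in the common text. No other section supplies a drug, dose or time for the experimental arm.

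**Step 2. The closing sentence of 9.2.** A noun appears to be missing after the verb. There are two plausible readings:

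- (a) No steroid, or other named drug, is injected, nor anything else that relieves pain. With a steroid as the missing noun, this contradicts the four add-on statements outright.
- (b) Nothing further is injected after a steroid already given. This would be consistent with the add-on design only if 9.2 contained an earlier steroid step, and it does not.

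The conflict therefore survives either reading, and it would remain if the sentence were deleted.

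**Step 3. The sample size, reproduced.** Inputs from Section 7.3: means 40 and 60 mm (difference 20 mm), SD 30 mm, two-sided 5%, power 90%, losses 20%.

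- Standardised difference = 20/30 = 0.667.
- Two-sample t-test (noncentral t): 48.26, rounded up to 49 evaluable per arm.
- 49 / (1 − 0.20) = 61.25, rounded up to 62 per arm, 124 in total. This matches the plan.
- Power with 49 evaluable per arm = 90.4%.

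The arithmetic is correct for the contrast it names, which is PRF plus steroid against steroid. The documents give no effect assumption for PRF alone against steroid.

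**Step 4. What a different contrast could do to power (illustration only).** Suppose effects are additive, every site follows 9.2, and withholding steroid reduces the 20 mm difference by the 6-month steroid effect. The documents do not give that effect, so a range is shown, with SD 30 mm and 49 evaluable per arm:

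| True difference | Reduction from 20 mm | Power |
|---|---|---|
| 20 mm | 0 mm | 90.4% |
| 17.15 mm | 2.85 mm | 80% |
| 15 mm | 5 mm | 69% |
| 10 mm | 10 mm | 37% |
| 5 mm | 15 mm | 13% |

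A reduction near zero is possible: inclusion criteria 7 and 3 require a previous epidural steroid injection and a VAS of at least 5. These figures show sensitivity and do not estimate the damage.

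**The case against.** The strongest reply is that the intent is clear. The sample size and the primary analysis both say PRF plus steroids, sites will read the Summary as well as Section 9, and compliance with the protocol means compliance with all of it. On that view 9.2 merely lost a line, and the closing sentence, being ungrammatical, proves little.

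Much of this is fair. Add-on is the more likely intent. The garbled sentence is weak evidence by itself, and a word could have been lost in drafting, in translation or when the file was read. A site reading the whole document meets a conflict and is not simply directed to PRF alone, so the figure of all 62 patients is a worst case. The four add-on statements are also not the only descriptions of the comparison: two of them sit in the same summary table, and the title, 5.1 and 7.1 omit the added steroid. The power range says nothing about how large the loss would be.

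The reply does not supply the missing step. Even a site that correctly infers the add-on design finds no drug, dose or timing for the experimental arm. The finding rests on that absence set against the four add-on statements, and neither depends on how the last sentence of 9.2 is read.

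**Conclusion.** The concern holds and should be fixed. The plan sizes and analyses PRF plus steroid against steroid, while its only experimental-arm procedure, followed as written, delivers PRF without steroid. The arms would then differ in two components instead of one, and the result could not be reported as the contrast in Section 13. If every site follows 9.2, this affects all 62 experimental patients of 124; if only some do, the estimate mixes the two contrasts.

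The conclusion needs no assumption about the size of the steroid effect. It would stand even if that effect were 0 mm at 6 months and power stayed at 90.4%, because the intervention and the contrast would still be undefined. The sample-size calculation itself is not at fault.

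**What to change.** Choose one contrast and state it throughout, before enrolment. The documents do not say whether enrolment has begun; if it has, first establish what each treated patient received.

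**Option A, add-on (recommended, because the sample size and primary analysis already assume it).**

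- Section 9.2: insert *After PRF at the last treated level, betamethasone 12 mg will be administered, as in 9.1*, with the same timing relative to the active or zero-voltage period in both arms.
- Section 9.2, closing sentence: replace with *No further substance capable of producing pain relief will be injected.*
- Title, Section 5.1 and Section 7.1: state PRF plus epidural steroids versus epidural steroids. Delete the reference to transforaminal placement in 7.1, a separate slip best corrected at the same time.

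**Option B, PRF alone.** State in 9.2 that no steroid is given and complete the closing sentence. Rewrite Summary items 9 and 12 and Sections 7.1, 7.3 and 13 as PRF versus steroid, and justify the 20 mm difference for that contrast.

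**Under either option,** record the substance and dose injected for every patient, unless the treatment CRF (not among these documents) already does so.

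**Cost.** Option A is a text amendment plus, if needed, two CRF data items (substance and dose), with no extra patients or visits. Option B costs the same in text, but the sample size would have to rise if a difference smaller than 20 mm is the defensible one.
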